9.7.2.3. Time to treatment changes

Kaplan-Meier analysis will be conducted to describe the following time-to-event outcomes for the treatment patterns as listed in [Table 3](#):

PFIZER CONFIDENTIAL

- Time to discontinuation of relugolix
- Time to switching to a different ADT treatment
- Time to add a new systemic PC treatment to relugolix

The number and proportion of patients with the corresponding event will be plotted over time and the number at risk table over time will be presented. The median time to event will be calculated.

9.7.3. Data analysis for Objective 3: To estimate adherence and persistence with relugolix among patients with PC who initiated relugolix

Adherence to relugolix as defined in [Table 3](#) will be described. MPR will be summarized over the entire exposure to relugolix during the follow-up period. PDC will be summarized within the 6, 12, and 18 months (tentatively, pending on the final length of follow-up) since the index date. Means, standard deviations, medians, and interquartile range will be estimated for adherence as a continuous variable. Counts and percentages will be estimated for adherence as a binary variable. Patients will be required to have complete follow-up data during the time to be included in each adherence calculation.

Persistence to relugolix as defined in [Table 3](#) will be described using Kaplan-Meier analysis since the index date. The number and proportion of patients persistent to relugolix will be plotted over time and the number at risk table over time will be presented.

9.7.4. Data analysis for Objective 4: To assess testosterone suppression and PSA responses among ADT naïve patients with PC who initiated relugolix

If sample size is sufficient, the count and percentage of patients with testosterone responses as defined in [Table 3](#) will be calculated among ADT naïve patients with at least one testosterone measure during the follow-up period. Similarly, if sample size is sufficient, the count and percentage of patients with PSA responses as defined in [Table 3](#) will be calculated among ADT naïve patients with at least one baseline and one follow-up period PSA measure.

9.7.5. Data analysis for Objective 5: To describe and compare demographics and clinical characteristics between Black and non-Hispanic White patients with PC who initiated relugolix

The same descriptive analysis described in [Section 9.7.1](#) will be conducted in Black and non-Hispanic White patients separately. If the sample sizes allow, SMD will be calculated to compare the patient baseline characteristics between Black vs. non-Hispanic White cohorts. Additionally, p-values from appropriate statistical tests (e.g., t-tests or rank-sum tests for continuous variables and chi-square tests for categorical variables) comparing Black vs. non-Hispanic White cohorts will be reported.

9.7.6. Data analysis for Objective 6: To describe and compare time to treatment changes between Black and non-Hispanic White patients with PC who initiated relugolix

The same descriptive analyses described in Section 9.7.2.3 will be conducted in Black and non-Hispanic White patients separately. Unadjusted and adjusted comparisons between the two race groups will be conducted. Cox proportional hazards (PH) regressions will be used to compare the time to treatment changes between the two race groups. Patient characteristics to be included in the adjusted models will be selected based on findings in Section 9.7.5 and clinical input.

9.7.7. Data analysis for Objective 7: To estimate and compare adherence and persistence with relugolix between Black and non-Hispanic White patients with PC who initiated relugolix

The same descriptive analyses described in Section 9.7.3 will be conducted in Black and non-Hispanic White patients separately. Unadjusted and adjusted comparisons between the two race groups will be conducted. Generalized linear models will be used to compare adherence to relugolix between the two race groups. Cox PH regressions will be used to compare persistence between the two race groups. Patient characteristics to be included in the adjusted models will be selected based on findings in Section 9.7.5 and clinical input.

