9. RESEARCH METHODS

9.1. Study design

This is a retrospective, observational study using January 1, 2006 – December 31, 2023 data from the National VA Health Care Network databases. PC patients who initiated relugolix will be selected based on diagnosis codes, age, treatment received, and continuous activity in the health care network. The identification period for relugolix use will be from December 18, 2020 to December 31, 2023. December 18, 2020 is the approval date for relugolix in the US, and December 31, 2023 is the end of available data. The index date will be defined as the initiation date of relugolix. The baseline period will be 365 days prior to the index date (hence the start of the study period is December 18, 2019). The follow-up period will be from the index date to the earliest of death, end of continuous eligibility or end of data availability. Most of the patient characteristics will be described during the baseline period. Certain patient characteristics will be described using all data available prior to the index date (i.e., data prior to December 18, 2019 will also be used if available; see more details in Table 2). Treatment patterns, adherence, and persistence with relugolix, and PSA and testosterone responses (if sample size allows) will be assessed during the follow-up period.

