Index treatment	
Index treatment regimens include:
 
 • Relugolix monotherapy • Relugolix + NSAA only (at least 90 days of NSAA use) • Relugolix + ARPI +/- NSAA (no chemotherapy) • Relugolix + ARPI + chemotherapy • Relugolix + chemotherapy +/- NSAA (no ARPI) • Relugolix + other (no ARPI, no chemotherapy) 
Index treatment regimen will be defined based on treatments received within 30 days before the index date and within 90 days after the index date.
 
Specific treatments included in each treatment category (i.e., ADT, NSAA, ARPI, chemotherapy, immunotherapy) are described in “Treatment history” in Table 2. Other treatments include immunotherapy, radium 223, olaparib, rucaparib, talazoparib, niraparib and lutetium Lu 177 vipivotide tetraxetan.
 
Number of patients who received any radiotherapy during the index treatment will be summarized.

Variable	Operational definition
Treatment patterns of relugolix	
Treatment patterns of relugolix include:
 
• Continued relugolix as in the index treatment (regardless of discontinuation of concomitant medications)• Continued relugolix with a new add-on systemic PC treatment (excluding ADT)• Discontinued relugolix and switched to another ADT treatment• Discontinued relugolix without switching to another ADT treatment 
Add-on systemic PC treatments include:
 
• ARPI• NSAA• Chemotherapy• Immunotherapy• Radium 223• Ketoconazole• Olaparib• Rucaparib• Talazoparib• Niraparib• Lutetium Lu 177 vipivotide tetraxetan 
Add-on therapy will be evaluated from 90 days after the index period to the end of the follow-up period.

Time to treatment changes	The time to treatment changes of interest include: 
• Time to discontinuation of relugolix• Time to switching to a different ADT treatment• Time to add a new systemic PC treatment to relugolix
Treatment adherence	Adherence to relugolix post the index date will be described using both MPR and PDC: 
• MPR: Sum of the days of supply divided by the number of days between the first fill and the end of the last refill (i.e., including the days of supply from the last refill)• PDC: Sum of the non-overlapping (i.e., not double counting of overlaps) days of supply covered

Variable	Operational definition

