	divided by a pre-determined period following treatment initiation (e.g., 6 and 12 months) Adherence will be described as a continuous variable and as a binary variable (<0.80: non-adherent, ≥ 0.80 : adherent)
Treatment persistence	Persistence to relugolix will be described as the proportion of patients who did not discontinue relugolix (i.e., with a treatment gap, switch to another ADT, or death; the minimum days of treatment gap, e.g., 45 or 60 days, will be finalized based on sample size and clinical input) during the follow-up period. Treatment gaps will be assessed from the end of the days of supply of the previous prescription to the earliest of the next prescription or the end of data availability.
PSA response	Only if sample size is sufficient and among patients with at least one baseline and one follow-up period PSA measure: 
• The number and percentage of patients with $\geq 50\%$ and $\geq 90\%$ decline from the baseline PSA to any PSA measurement during the follow-up period and while on relugolix• The number and percentage of patients with the nadir PSA value during the follow-up period and on treatment of relugolix < 0.01, 0.1, and 0.2 ng/mL
Testosterone response	Only if sample size is sufficient and among patients with at least one follow-up period testosterone measure: 
• The number and percentage of patients with at least one testosterone value of <50ng/dL and <20 ng/dL during the follow-up period and while on relugolix 
If sample size is sufficient, the analysis above may be conducted among patients with at least one baseline and one follow-up period testosterone measure

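### Kaplan-Meier for switching and add-on overstates the plotted proportions: slightly through censoring at death, materially for add-on if stopping relugolix is also censored, which the plan leaves open

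*Combined protocol and SAP*

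**What the plan says.** Section 9.7.2.3 states: "Kaplan-Meier analysis will be conducted to describe the following time-to-event outcomes for the treatment patterns as listed in" Table 3. Two of the three outcomes are "Time to switching to a different ADT treatment" and "Time to add a new systemic PC treatment to relugolix". For each, "The number and proportion of patients with the corresponding event will be plotted over time", with a number-at-risk table and a median. Section 9.7.6 repeats the curves for Black and non-Hispanic White patients and compares the two groups by Cox regression.

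The only general rule that can end time at risk is in Section 9.1: "The follow-up period will be from the index date to the earliest of death, end of continuous eligibility or end of data availability". Death counts as an event in one place, the persistence definition in Table 3, which covers patients who "did not discontinue relugolix (i.e., with a treatment gap, switch to another ADT, or death". No such rule is given for switching or add-on.

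Table 3 also defines the patterns. Switching is "Discontinued relugolix and switched to another ADT treatment", so stopping is part of that event. Add-on requires that relugolix continues. Stopping without a switch is a separate pattern. Add-on is assessed from 90 days to the end of follow-up, not to the end of relugolix. No competing-risk method appears anywhere in the document.

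**The concern.** Kaplan-Meier treats a censored patient as someone who could still have the event later. That is reasonable at the end of data availability, but not at death, after which neither a switch nor an add-on is possible. It is also doubtful for add-on once relugolix has stopped, because a patient no longer taking relugolix cannot have something added to it unless relugolix is restarted. Where such events are censored, one minus Kaplan-Meier estimates the proportion who would have the event if the competing events did not exist. The plan promises something else: the proportion of patients with the event.

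At stake are the absolute proportions and medians for Objectives 2 and 6. Because the handling of stopping is unwritten, two analysts following Section 9.7.2.3 could also produce visibly different add-on curves from the same data. The by-race curves would be distorted unequally if death or stopping differs by race.

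**Working it through.** The plan states no event rate, so it has no figure to reproduce. The check compares the two estimands under assumed rates.

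**Inputs (all assumed).** The 12-month risk of each event acting alone is 20% for the event of interest, 5% for death and 30% for stopping. With constant, independent hazards, h = −ln(1 − risk) per year:

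- event: −ln(0.80) = 0.2231
- death: −ln(0.95) = 0.0513
- stopping: −ln(0.70) = 0.3567

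**Formulas.** Let h be the event hazard, c the total competing hazard and t the time in years.

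- One minus Kaplan-Meier, competing events censored: 1 − exp(−h·t)
- Cumulative incidence: h/(h + c) × [1 − exp(−(h + c)·t)]

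**Death as the only competing event.** h + c = 0.2744, and event-free survival at one year is 0.80 × 0.95 = 0.76.

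- 12 months: 0.2231/0.2744 × (1 − 0.76) = 0.8131 × 0.24 = 19.5%
- 24 months: 0.8131 × (1 − 0.76²) = 0.8131 × 0.4224 = 34.3%

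**Death and stopping both competing (add-on).** h + c = 0.6311, and event-free survival at one year is 0.80 × 0.95 × 0.70 = 0.532.

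- 12 months: 0.2231/0.6311 × (1 − 0.532) = 0.3536 × 0.468 = 16.5%
- 24 months: 0.3536 × (1 − 0.532²) = 0.3536 × 0.7170 = 25.4%

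| Months | 1 − KM | Cumulative incidence, death competing | Overstatement (points) | Cumulative incidence, death and stopping competing | Overstatement (points) |
|---|---|---|---|---|---|
| 12 | 20.0% | 19.5% | 0.5 | 16.5% | 3.5 |
| 18 | 28.4% | 27.4% | 1.0 | 21.6% | 6.8 |
| 24 | 36.0% | 34.3% | 1.7 | 25.4% | 10.6 |

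**Other reading for add-on.** If stoppers remain in the risk set without being able to have the event, and only death is censored, a simulation of 400,000 patients at these rates gave about 17.0% at 12 months. The simulated cumulative incidence was 16.6%. Most of the overstatement disappears, but the number-at-risk table then counts patients who cannot have the event. The choice of rule alone moves the 12-month figure from about 17.0% to 20.0%.

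**Range.** With 12-month risks of 10–30% (event), 3–10% (death) and 10–40% (stopping):

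- death alone censored: 0.1 to 1.4 points at 12 months, 0.5 to 4.4 at 24 months
- death and stopping censored: 0.6 to 7.2 points at 12 months, 2.3 to 19.6 at 24 months

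**Median.** Take risks of 30% (event), 5% (death) and 30% (stopping). With death and stopping censored, one minus Kaplan-Meier is 51.0% at 24 months, so a median would be reported. Cumulative incidence is 36.5% at 24 months and can never exceed 0.3567/(0.3567 + 0.0513 + 0.3567) = 46.6%, so no median exists.

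**Time axis.** The formulas start the clock at zero. Add-on is assessed only from 90 days, so for that outcome the times are best read as time since assessment begins. The direction does not change.

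**The case against.** The strongest objection is that nothing in the document censors patients when they stop relugolix. Follow-up ends only at death, end of eligibility or end of data, and add-on is assessed to the end of follow-up. Read literally, stoppers stay in the risk set, only death is censored, and the overstatement is small at the base-case rates. This stands. A reader might infer from the add-on definition that the plan censors at stopping and that all the plotted proportions are badly inflated. The text does not support that: it is silent on stopping, and the larger figures apply only under one of the two possible rules.

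A second objection concerns switching, and it also stands. A switch includes stopping and can follow a treatment gap. Whether a patient has stopped without switching is known only from later follow-up. Treating a gap as a terminal competing event would lose later switches, and classifying patients by what happened later would condition on the future. Stopping therefore should not compete with switching.

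Third, Objectives 2 and 6 are exploratory, no hypotheses are specified, and Section 9.7.2.2 separately reports the number and proportion in each of the four patterns. This limits the severity. Those crude proportions do not replace a time-based estimate, however, because length of follow-up varies between patients.

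**Conclusion.** The point holds in a limited form. Kaplan-Meier does not estimate the proportion that Section 9.7.2.3 says will be plotted. For switching, the overstatement comes from death and is small: about 0.5 points at 12 months and 1.7 at 24 months in the base case. For add-on it is equally small or material (3.5 points at 12 months, 10.6 at 24 months), depending on a rule the plan does not state. The upward direction does not depend on the assumed rates; the sizes do, and they also assume constant and independent hazards.

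Two further inferences would go too far. The Cox comparison is not invalid: it can stay, provided it is read as cause-specific. Unequal distortion by race is a possibility only, since the documents give no rates of death or stopping by race. For exploratory objectives, this is a change that should be made because it is cheap, not a flaw that undermines the study.

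**What to change.** In Sections 9.7.2.3 and 9.7.6, replace Kaplan-Meier for switching and add-on with Aalen-Johansen cumulative incidence, and write the event, censoring and competing events for each outcome:

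- **Add-on:** death and relugolix discontinuation are competing events. Time at risk starts when add-on assessment starts (90 days), and the report states that the denominator is patients alive and still on relugolix then. Discontinuation is defined as for persistence in Table 3.
- **Switching:** death is the competing event. Patients stay at risk after a treatment gap, so that later switches count.
- **Reporting:** give cumulative incidence at 6, 12 and 18 months, the time points already planned for PDC, and a median only if cumulative incidence reaches 50%.
- **Race comparison:** use the same risk sets in the Cox models and label the hazard ratios cause-specific.

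The cost is about a paragraph of protocol text and a standard procedure in SAS 9.4, which the plan already names; no new data are needed. The downside is slightly lower reported percentages (more for add-on if stopping would otherwise have been censored), and medians that may not be estimable.

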9.8. Quality control

Best practice guidelines will be followed to ensure project quality, including structured organization of project materials (e.g., data extracts, statistical software programs, output tables) and standard internal audit process. The audit process both confirms the validity of the analytical approach and ensures that all programs and results are accurate.

9.9. Limitations of the research methods

The analyses conducted as part of this study are subject to the following limitations, which will be addressed in any write-up of the study:

- As this study will be conducted among veterans, its findings may not be generalizable to other populations
- Certain assumptions will be made in order to depict treatment patterns. However, the definition of treatment patterns will nevertheless be subject to assumptions that may not match up to the prescribing physicians' intent
- Data are subject to inaccuracies in coding of diagnoses. The presence of a diagnosis code in the data does not necessarily mean the presence of disease. The disease may be incorrectly coded, or the code was included as a rule-out criterion
- The presence of a prescription does not necessarily mean the medication was consumed as prescribed. In addition, prescriptions filled over the counter or provided as samples by the physician are not included in the data

- The fact that our entry criteria is at least 2 subscriptions of relugolix means we are selecting patients who were able to tolerate the first month and followed up to receive a second month. How this cohort relates to all patients given relugolix is unknown.

9.10. Other aspects

Not applicable.

10. PROTECTION OF HUMAN SUBJECTS

This study involves data that exist in anonymized structured format and contain no patient personal information.

10.1. Patient information

This study involves data that exist in anonymized structured format and contain no patient personal information.

10.2. Patient consent

As this study involves anonymized structured data, which according to applicable legal requirements do not contain data subject to privacy laws, obtaining informed consent from patients by Pfizer is not required.

10.3. Institutional review board (IRB)/Independent ethics committee (IEC)

An IRB waiver was received.

10.4. Ethical conduct of the study

The study will be conducted in accordance with legal and regulatory requirements, as well as with scientific purpose, value and rigor and follow generally accepted research practices described in Guidelines for Good Pharmacoepidemiology Practices issued by the International Society for Pharmacoepidemiology.

11. MANAGEMENT AND REPORTING OF ADVERSE EVENTS/ADVERSE REACTIONS

This is a retrospective analysis using anonymized National VA Health Care Network database. In the data, individual patient data are not retrieved or validated, and it is not possible to link (i.e., identify a potential association between) a particular product and medical event for any individual. Thus, the minimum criteria for reporting an adverse event (i.e., identifiable patient, identifiable reporter, a suspect product, and event) cannot be met.

12. PLANS FOR DISSEMINATING AND COMMUNICATING STUDY RESULTS

In the event of any prohibition or restriction imposed (e.g., clinical hold) by an applicable competent authority in any area of the world, or if the investigator is aware of any new information which might influence the evaluation of the benefits and risks of a Pfizer product, Pfizer should be informed immediately.

ANNEX 1. LIST OF STAND-ALONE DOCUMENTS

None.

ANNEX 2. ADDITIONAL INFORMATION

Appendix Table 1. Codes for PC treatments

	GPI	HCPCS/CPT	ICD
ADT			
		CPT 54520, 54522, 54530, 54535, 54690	ICD-10-CM Z90.79
Orchiectomy			ICD-10-PCS 0V590ZZ, 0V593ZZ, 0V594ZZ, 0V5B0ZZ, 0V5B3ZZ, 0V5B4ZZ, 0V5C0ZZ, 0V5C3ZZ, 0V5C4ZZ, 0VT90ZZ, 0VT94ZZ, 0VTB0ZZ, 0VTB4ZZ, 0VTC0ZZ, 0VTC4ZZ
LHRH agonists/antagonists			
Degarelix	2140552510	J9155	
Goserelin	21405005	J9202	
Histrelin	2140500710	J1675, J9225, J9226, S0133	
Leuprorelin	21405010	J1950, J9217, J9218, J9219, Q0057	
Relugolix	21405570000320, 24993503800320		
Triptorelin	21405050	J3315	
ARPI			
Apalutamide	2140241000		
Abiraterone	2140601020		
Darolutamide	2140242500		
Enzalutamide	2140243000		
NSAA			
Bicalutamide	2140242000		
Flutamide	2140244000		
Nilutamide	2140246000		
Chemotherapy		HCPCS	ICD
Cabazitaxel	2150000300	C9276, J9043	
Docetaxel	2150000500	J9170, J9171	
Carboplatin	2110001500	J8530, J9070, J9080, J9090, J9091, J9092, J9093, J9094, J9095, J9096, J9097	

PFIZER CONFIDENTIAL

CT24-WI-GL02-RF02 5.0 Non-Interventional Study Protocol Template For Secondary Data Collection Study 01-Aug-2023

Page 35 of 41

Cisplatin	2110002000	J9045	
Oxaliplatin	2110002800	J9263	
Mitoxantrone	2120005500	J9293	
Immunotherapy		HCPCS	ICD
Sipuleucel-T	2165107000	Q2043, C9273	
Pembrolizumab	21357953002	J9271, C9027	
Others		HCPCS	ICD
Radium-223	2160005500	A9606	
Ketoconazole	1140404000, 9630106400, 9015404500		
Olaparib	21535560		
Lutetium Lu 177 vipivotide tetraxetan	21600045802020	A9607	
Niraparib	21535550200, 21409902120		
Talazoparib	215355804001		
Niraparib	21535550200, 21409902120		
Rucaparib	21535570		

Abbreviations: ADT: androgen deprivation therapy; ARPI: androgen receptor pathway inhibitor; CTP: Current Procedural Terminology; GPI: Generic Product Identifier; HCPCS: Healthcare Common Procedure Coding System; ICD: International Classification of Diseases; ICD-10-CM: International Classification of Diseases, 10th Revision, Clinical Modification; ICD-10-PCS: International Classification of Diseases, 10th Revision, Procedures; LHRH: luteinizing hormone-releasing hormone; NSAA: non-steroidal anti-androgen

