 2. To assess treatment patterns among patients with PC who initiated relugolix
 3. To estimate adherence and persistence with relugolix among patients with PC who initiated relugolix
 4. To assess testosterone suppression and prostate-specific antigen (PSA) responses among ADT naïve patients with PC who initiated relugolix
 5. To describe and compare demographics and clinical characteristics between Black and non-Hispanic White patients with PC who initiated relugolix
 6. To describe and compare time to treatment changes between Black and non-Hispanic White patients with PC who initiated relugolix
 7. To estimate and compare adherence and persistence with relugolix between Black and non-Hispanic White patients with PC who initiated relugolix

Study Design: The current study will be a retrospective data analysis to describe patient characteristics, treatment patterns, adherence, and persistence among patients with PC who initiated relugolix. Adult (aged ≥ 18 years) male patients with PC who had relugolix (initiation date as the index date) will be selected from the National Veterans Affairs (VA) Health Care Network databases. Patients will be required to have continuous eligibility for at least 365 days prior to the index date and 90 days after the index date (unless died within 90 days). The baseline period will be the 365 days prior to the index date. The follow-up period will be from the index date to the earliest of death, end of continuous eligibility or end of data availability.

Population: The overall population will include PC patients who initiated relugolix. The following sample selection criteria will be used:

- Inclusion criteria:
 - Male with ≥ 1 diagnosis for PC
 - Had ≥ 2 prescriptions of relugolix on or after the first observed PC diagnosis. The identification period for relugolix use will be from December 18, 2020 to December 31, 2023
 - Index date: the initiation date of relugolix
 - At least 18 years old at the index date
 - Had continuous activity in the data for at least 365 days before the index date and 90 days following the index date (unless died within 90 days)
- Exclusion criteria:
 - Had surgical castration (bilateral orchiectomy) any time before the index date
 - Participated in clinical trials within 30 days prior to or 90 days after the index date
 - Had any other primary cancer (excluding non-melanoma skin cancer) during the baseline period

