9.2.2. Exclusion criteria

Patients will not be included from the study if they:

[figure not shown]
- Had surgical castration (bilateral orchectomy) any time before the index date

PFIZER CONFIDENTIAL

CT24-WI-GL02-RF02 5.0 Non-Interventional Study Protocol Template For Secondary Data Collection Study 01-
Aug-2023
Page 17 of 41

- Had evidence of clinical trial participation within 30 days prior to the index date or within 90 days since the index date
- Had any other primary cancer (excluding non-melanoma skin cancer) during the baseline period

Figure 1. Sample selection for PC patients initiated relugolix

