9.3. Variables

Baseline variables (Table 2) will be measured during the baseline period (365 days prior to the index date). Treatment patterns, adherence and persistence, and clinical variables (Table 3) will be measured during the follow-up period.

Table 2. Baseline demographic and clinical characteristic variables

Variable	Operational definition
Age	Age will be defined as of the index date and retained in the dataset as a continuous variable and a categorical variable (e.g., ≤ 59 , 60-69, 70-79, ≥ 80 years old).
Race/ethnicity	Proportion of patients that were non-Hispanic White, Black, Hispanic, other or unknown will be summarized.
Geographic regions	Proportion of patients that lived in Northeast, Midwest, South and West areas will be summarized.
Index year	A categorical variable for the index calendar year will be summarized.
Site of metastasis	Proportion of patients that had a metastatic diagnosis at the following sites: bone only, bone and node only, node

PFIZER CONFIDENTIAL

Variable	Operational definition
	only, viscera and other, will be summarized among patients with metastatic PC. All data available prior to the index date will be used.
Treatment history	
Proportion of patients who had each of the following treatments in the baseline period will be evaluated:
 
• Prostatectomy• Chronic oral corticosteroid use• Pain medication (opioids)• ADT treatment (leuprolide, degarelix, goserelin, histrelin, triptorelin)• Androgen receptor pathway inhibitor (ARPI; abiraterone, apalutamide, darolutamide, enzalutamide)• Non-steroidal anti-androgen (NSAA; bicalutamide, nilutamide, flutamide)• Chemotherapy (docetaxel, cabazitaxel, carboplatin, oxaliplatin, cisplatin, mitoxantrone)• Immunotherapy (sipuleucel-T, pembrolizumab)• Radium 223• Systemic ketoconazole• Olaparib• Rucaparib• Talazoparib• Niraparib• Lutetium Lu 177 vipivotide tetraxetan• Radiotherapy 
Treatments considered as a part of index treatment regimen will not be flagged as baseline treatments if received within 30 days prior to index date.

Time from first observed PC diagnosis date to the index date	Time from the first observed PC date in the data to the index date will be evaluated. All data available prior to the index date will be used.
NCI Charlson Comorbidity Index (CCI) score	The NCI version of the CCI score will be created during the baseline period.

Variable	Operational definition

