9.5. Study size

As no priori hypotheses are specified, sample size calculations are not applicable. The number of patients eligible for the study will be determined in accordance with the sample selection conducted per the criteria described in Section 9.2.

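### The only orchiectomy code list is wider than the bilateral-only exclusion it has to implement, and no rule says which codes or combinations count

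*Combined protocol and SAP*

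**What the plan says.** Section 9.2.2 removes men who "Had surgical castration (bilateral orchectomy) any time before the index date". The Abstract gives the same criterion, also limited to bilateral surgery. The look-back has no lower limit other than the start of the data, January 1, 2006 (sections 9.1 and 9.4).

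Appendix Table 1 in Annex 2 has one row for orchiectomy, placed under ADT. It contains:

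- CPT: "54520, 54522, 54530, 54535, 54690"
- ICD-10-CM: Z90.79
- ICD-10-PCS: "0V590ZZ, 0V593ZZ, 0V594ZZ, 0V5B0ZZ, 0V5B3ZZ, 0V5B4ZZ, 0V5C0ZZ, 0V5C3ZZ, 0V5C4ZZ", followed by "0VT90ZZ, 0VT94ZZ, 0VTB0ZZ, 0VTB4ZZ, 0VTC0ZZ, 0VTC4ZZ"

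The row prints no code descriptors. It sets no laterality or modifier requirement and no rule for pairing a right-side with a left-side record. Section 9.2.2 adds none.

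Table 2 (section 9.3) says under treatment history: "Proportion of patients who had each of the following treatments in the baseline period will be evaluated". Prostatectomy is the first entry in that list and is not among the exclusions in section 9.2.2.

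Section 9.5 leaves the cohort to the selection rules: "The number of patients eligible for the study will be determined in accordance with the sample selection conducted per the criteria" of section 9.2.

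**The concern.** The criterion is narrow and the list is broad. A programmer who is handed the list without a combination rule could reasonably flag any man with any listed code. Because the look-back is open-ended, one old record would then be enough.

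This matters because the primary objective is to describe who starts relugolix. A man wrongly dropped at entry cannot be recovered in a later analysis. If the losses fall on men with a prior prostatectomy, the described cohort could shift on characteristics that go with that history, such as time since first diagnosis or baseline PSA. The limitations in section 9.9 mention inaccurate diagnosis coding in general, but not a difference between the exclusion and its code list.

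**Working it through.** The plan states no figure on this point, so the check compares the criterion with the list.

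**1. Does this row serve the exclusion?** It is the only orchiectomy list, and Annex 1 names no stand-alone document that could hold another. No other use is evident: the ADT entry in Table 2 lists drugs only, ADT-naïve status is defined by LHRH agonists and GnRH antagonists, and Table 3 refers back to Table 2 for its treatment categories.

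**2. Count of the ICD-10-PCS codes by fourth character.**

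| Fourth character | 0V5 codes | 0VT codes | Total |
|---|---|---|---|
| 9 | 3 | 2 | 5 |
| B | 3 | 2 | 5 |
| C | 3 | 2 | 5 |
| All | 9 | 6 | 15 |

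The suffixes are identical across the three sets (0ZZ, 3ZZ, 4ZZ for 0V5; 0ZZ, 4ZZ for 0VT), so only the fourth character separates them. In ICD-10-PCS, the classification named in the appendix, 9, B and C are right testis, left testis and bilateral. On that reading 10 of 15 codes are one-sided and 5 are bilateral. This describes the list. It is not a misclassification rate.

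**3. CPT codes.** The row gives five codes with no side. In the CPT classification 54522 is partial orchiectomy, and 54530 and 54535 are radical orchiectomy for tumour. None of these alone shows that both testes were removed.

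**4. ICD-10-CM code.** Z90.79 is the residual status code for acquired absence of other genital organs. It carries no side, is not specific to the testes, and also covers an absent prostate.

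**5. Effect of two possible rules on the same records.**

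| Record before index | Any listed code suffices | Evidence of both sides required |
|---|---|---|
| One 0V5C or 0VTC code | excluded | excluded |
| One right-side and one left-side code | excluded | excluded |
| One right-side code only | excluded | kept |
| 54522 only | excluded | kept |
| Z90.79 only, after prostatectomy | excluded | kept |

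The last three men do not meet section 9.2.2 on this evidence. The protocol does not say which column applies.

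**6. Size.** The share of otherwise eligible men removed through Z90.79 would be p × q, where p is the share with a prior prostatectomy and q is the share of those carrying the code. The documents give neither. With p assumed at 10–40% and q at 10–80%, the product runs from 0.10 × 0.10 = 1% to 0.40 × 0.80 = 32%. That range is too wide to size the problem, and nothing below relies on it.

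**The case against.** The strongest reply is that the governing text says bilateral, so following the protocol as written includes applying that word to the list. Appendix Table 1 is an inventory of codes and states no trigger rule. One-sided codes also belong in such an inventory, because two separate one-sided operations can add up to castration. The code meanings come from outside classifications, as the appendix prints no descriptors. Figure 1, the sample-selection figure, is not reproduced in the text reviewed, so any detail in it could not be checked.

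Much of this stands. A reader might infer that the plan will exclude everyone with a listed code, or that the 10 one-sided codes are mistakes. The documents support neither reading. What is missing is the rule that turns codes into a bilateral finding.

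A reader might also infer a large fall in the reported prostatectomy share. The documents do not support that either. They give no prevalence of prior prostatectomy or of Z90.79, and Table 2 reports prostatectomy only within the 365-day baseline period, so no planned output shows lifetime prostatectomy.

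The reply does not remove the mismatch. The protocol uses the named classifications as its operational definitions, so their meanings can be looked up. No rule for combining codes can make a non-lateral residual status code show bilateral castration.

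**Conclusion.** The operational list is wider than the criterion, and the protocol has no rule to close the gap. If one listed code is taken as sufficient, men who do not meet section 9.2.2 would be excluded, including some with a prior prostatectomy whom Table 2 treats as eligible. This rests on two assumptions: that the standard ICD-10-PCS, CPT and ICD-10-CM meanings apply, and that no combination rule is given in the unseen figure. The mismatch is clear on those terms, but the number of men affected and the resulting shift in any estimate are unknown. The documents do not show that the adherence, persistence or race comparisons would be biased. It should be corrected before the cohort is drawn, because it governs entry and costs little to repair.

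**What to change.** Before the cohort pull, give the section 9.2.2 exclusion its own code list, with descriptors, and accept as evidence of bilateral orchiectomy:

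- a bilateral ICD-10-PCS code (0V5C- or 0VTC-); or
- a right-side code plus a left-side code; or
- an orchiectomy CPT code with evidence that both sides were treated, where the VA data carry it. Section 9.4 does not say whether they do.

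State that Z90.79, 54522, a single one-sided code, or a single unmodified CPT code (including 54530 and 54535) does not trigger exclusion alone. Report the number excluded by code, and the number that the printed list would have excluded but the new list keeps. That second count supplies the size that is now unknown.

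The cost is a code-list edit. The downside is that a few castrated men known only by a status code or an unmodified code may be kept. This matters most for Objective 4: ADT-naïve status is defined by drugs alone, so such a man could enter that analysis with testosterone already low and be counted as a response. A sensitivity analysis that excludes the men with only such codes, run for the baseline description and the testosterone endpoint, would show the effect.
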